2.2.5.2 Core Lab Simulations

Note that simulations described in this protocol with respect to endpoint determination will be done only by the core lab near the end of the study based on information collected during actual study windows.

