2.2.2.2 PRIMARY EFFECTIVENESS ENDPOINT

The primary effectiveness endpoint will be evaluated in subjects with prostate cancer who are undergoing radiotherapy by means of IMRT and who receive the balloon, with individual patient success defined as a reduction of at least 25% of the volume of the rectum receiving greater or equal to 70 Gy (V_{Rectum} 70) when compared to pre-implantation values. The study will be considered a success if the rate is significantly greater than 75%; the hypothesis will be evaluated using a one-sided exact binomial test as detailed in **Section 2.3**.

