2.2.5 STUDY DESIGN

2.2.5.1 OVERALL STUDY DESIGN

This study will be a prospective, multi-center, randomized, double-arm, single blind, concurrently controlled study to assess the safety and efficacy of the BioProtect Balloon Implant System in prostate cancer subjects undergoing radiotherapy by means of IMRT.

Subjects will be randomized in a 2:1 ratio (balloon implantation:control) to receive either IMRT +marking + balloon implantation or IMRT +marking. The balloon will be inserted during the same session of the marking.

Subjects will be blinded to study assignments. It is not practical to blind the surgeon or surgeon's staff since they will participate in the insertion procedure and/or be responsible for

maintaining source documentation. Additionally, the core lab cannot be blinded since the balloon will be visible on the CT images.

All subjects enrolled in the study will be included in an "intent-to-treat" analysis regardless of failure to complete the required follow-up examinations. Subjects will be considered enrolled in the study for the purposes of an intent-to-treat analysis only after they have provided Informed Consent and have been randomized. Preliminary data will be captured for subjects excluded intraoperatively, documenting the reason(s) for exclusion. It is anticipated that very few, if any, subjects will be excluded intraoperatively. Sites will maintain a log of screening failures, documenting the reason for failure. Additionally, subjects who are randomized but not implanted (e.g., due to an adverse event that prevents or significantly delays their radiation treatment) may be removed from the study. Such removals will be documented and reported appropriately. Subjects who are screening failures or who are removed from the study prior to implantation will be excluded from analysis.

This study will utilize a core laboratory for analysis of CT images. Post implantation CT images for the *Balloon Group* will be compared to pre-implantation images to demonstrate the change in distance and potential for rectal protection provided by the balloon.

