2.3.6.2 MINIMIZATION OF RISKS

Adequate measures have been taken to minimize all of the above risks prior to initiation of a U.S. pivotal clinical study, including proper design specification and review, preclinical testing, and clinical evaluations within and outside the United States.

BioProtect will provide appropriate training to each investigator prior to each site's respective study initiation. Investigators will be trained on the technique, selection criteria, and protocol for the clinical study prior to their first implantation procedure. The training will address topics such as the indications and contraindications for the use of the device, the implantation procedure, the study contouring and dosing calculations, follow-up care and management of adverse events.

The initial balloon implantations will be done with the supervision of a BioProtect representative and after a methodic training conducted by BioProtect. The number of procedures proctored will be at least one per implanting physician. Each site will be notified when the Sponsor is satisfied that a Sponsor representative presence is no longer required.

Training will include thorough reading of the IFU, an in vitro demonstration, thorough review of the training video presenting a full procedure on a human case and doing a procedure under the supervision of a Proctor.

Investigators will assess the possible presence of the risks associated with the balloon implant during the implantation procedure, and at each IMRT/follow-up visit by physical and/or radiologic examination and subject interview as applicable.

BioProtect will train and assign monitors to verify that appropriate data is recorded for all study subjects for whom Informed Consent is obtained; and that no study procedures are administered without Informed Consent. A core lab will review radiographic films/digital files to ensure a non-biased evaluation of radiographic endpoints. BioProtect will appoint a qualified radiation oncologist to evaluate potential safety issues and to oversee and review medical monitoring issues. Additionally, a CEC will be appointed to evaluate and adjudicate adverse event data prior to submission of the marketing application.

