# 5 Investigational Plan and Study Design

This study is a prospective, multi-center, randomized, double-arm, single blind, concurrently controlled study of the ProSpace Balloon in prostate cancer subjects undergoing radiotherapy by means of IMRT. Subjects will be randomized in a 2:1 ratio (balloon implantation:control) to receive either IMRT + marking + ProSpace implantation or IMRT + marking. Subjects in the Balloon Implantation Group (*ProSpace Group*) will have the ProSpace Balloon inserted during the same session as the marking.

Subjects will be evaluated Pre-operatively; at marking/implantation; Post-marking/implantation; weekly during IMRT Visits (no window); at 6 months post marking/implantation ( $\pm 2$  weeks); and every 6 months thereafter ( $\pm 4$  weeks) until the last subject enrolled is due for his 6-month evaluation. There will be no interim analysis performed during the clinical study.

The study will utilize a core laboratory for analysis of CT images. Post-implantation CT images for the *ProSpace Group* subjects will be compared to the subjects' own pre-implantation images to demonstrate the change in distance and the potential for rectal protection provided by the balloon. CT will be taken

Statistical Analysis Plan	Client/Project	BioProtect BP-007
	Version and Date	V2 05-DEC-2021

for the *ProSpace Group* up to 30 days pre-implantation, post-implantation, at the last XRT visit, and at the 6-month follow-up visit. CT may also be taken in the *ProSpace Group* at 12 months if remnants of the balloon remain at 6 months.

Two hundred twenty-two (222) men will be enrolled at up to 25 sites in the US and outside the US, with no more than 40 subjects enrolled per site. A blocked randomization, with randomly varying block sizes, will be used, to minimize the likelihood that the site will be able to infer the next randomization assignment in the sequence.

Subjects will be blinded to study assignments. The surgeon, surgeon's staff, and core lab cannot be blinded due to the nature of the marking/implantation procedure and device.

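### Neither the protocol nor the SAP prevents the pre-implant V70, the denominator of the co-primary efficacy endpoint, from being drawn or revised with knowledge of the post-implant scan

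*Protocol*

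**What the plan says.** - **Endpoint.** Protocol section 2.2.2.2 has "individual patient success defined as a reduction of at least 25% of the volume of the rectum" that receives 70 Gy or more, "when compared to pre-implantation values". The pre-implant V70 is therefore the denominator of each man's result.
- **Blinding.** Protocol section 2.2.5.1 says that "the core lab cannot be blinded since the balloon will be visible on the CT images". SAP section 5 says the "core lab cannot be blinded due to the nature of the marking/implantation procedure and device". Neither separates the pre-implant from the post-implant CT.
- **Timing.** Protocol section 2.2.5.2 says: "simulations described in this protocol with respect to endpoint determination will be done only by the core lab near the end of the study". The same sentence adds that they draw on data gathered within the visit windows. The scans are prospective; the simulations are late.
- **Which scans exist.** Under protocol section 2.2.6.3 the Balloon Group has a CT in the 30 days before implantation and another after it. The Control Group has only the post-implantation CT.
- **Post-implant simulation.** Protocol section 2.2.6.7.1 bases it on the planning images. SAP section 7 places those images 3 to 21 days after marking.
- **Stated aim.** Protocol section 2.3.6.2 says: "A core lab will review radiographic films/digital files to ensure a non-biased evaluation of radiographic endpoints". It gives no procedure for this.
- **Not found in either document.** A reading order, a lock on the baseline contour or plan, separate readers for the two scans, or an audit trail for changes.

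**The concern.** The reason given for an unblinded core lab applies to only one scan of each pair. A CT taken before implantation shows no balloon, so its reader could be kept from knowing how much space was later achieved. The plan does not require this, and it schedules the simulations for a time when both scans are available.

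Several features leave this endpoint exposed. The treatment plan is built on the post-implant CT, and no clinical plan on the pre-implant CT is described, so there is nothing independent against which to check the baseline simulation. The efficacy test is single-arm, so no concurrent comparison cancels a reader effect. The planned sensitivity analysis for efficacy (protocol section 2.3.4.3, SAP section 10.3.4.2.3) varies only missing values. The secondary dosimetry is also compared with baseline within the balloon arm, so it is not independent confirmation. A generous contour or a less optimised plan on the pre-implant CT would make a 25% fall easier to reach, and no planned analysis would show it.

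**Working it through.** **1. The plan's own figure.** Inputs: n = 136 evaluable balloon subjects and true rate 87.5% (protocol section 2.3.4.4.1); null rate 75% and one-sided exact binomial test at 0.025 (section 2.3.4.3).

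- The smallest r with P(X ≥ r | 136, 0.75) ≤ 0.025 is r = 113, which is 113/136 = 83.1%.
- Actual size: P(X ≥ 113 | 136, 0.75) = 0.0159.
- Power: P(X ≥ 113 | 136, 0.875) = 0.949. The stated 95% reproduces to rounding, and no figure in the plan is disputed.

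**2. Does the stated reason cover the pre-implant CT?** The reason is that the balloon is visible. The pre-implant CT precedes the balloon. The reason fails for that scan.

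**3. Could the post-implant scan be known when the baseline is simulated?** Post-implant images are due by day 21 after marking, and endpoint simulations run near the end of the study. Both scans of each man therefore exist by then, and no rule keeps the second from the reader of the first.

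**4. How sensitive is the test to the denominator?** Assumptions not in the documents: log(post/pre V70) is normal with SD 0.6 or 1.0; the true success rate is exactly 75%; every pre-implant V70 is too high by a fraction k.

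- True reduction needed to be scored a success: 1 − 0.75(1 + k), which is 21.3%, 17.5% and 13.8% for k = 5%, 10% and 15%.
- Scored success probability: p = Φ(0.6745 + ln(1 + k)/SD).
- Chance of declaring success: P(X ≥ 113 | 136, p).

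| k | SD 1.0: p | SD 1.0: false success | SD 0.6: p | SD 0.6: false success |
|---|---|---|---|---|
| 0 | 0.750 | 1.6% | 0.750 | 1.6% |
| 5% | 0.765 | 4.0% | 0.775 | 6.9% |
| 10% | 0.779 | 8.6% | 0.798 | 19.7% |
| 15% | 0.792 | 15.7% | 0.818 | 39.8% |

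The effect is smaller if fewer men are affected. With k = 10% in a random quarter of men, false success is 2.5% (SD 1.0) to 3.3% (SD 0.6); in half of them, 3.9% to 6.5%.

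**5. Without a distribution.** At 75% the expected count is 0.75 × 136 = 102, which is 11 short of 113. Adding 3 men in 136 to the success rate gives p = 0.75 + 3/136 = 0.772 and false success 5.9%. Adding 5 men gives p = 0.787 and 12.3%.

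**6. What these figures do not show.** Step 4 inflates baselines whatever the man's post-implant result. A reader who never saw a post-implant scan could produce the same inflation. The table measures sensitivity to baseline bias from any source, not the effect of reading order.

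**The case against.** A reader might infer that the denominator is in fact drawn with the outcome in hand. The documents do not say that. They do not say that one reader opens both scans, that baseline work follows post-implant work, or that a finished baseline may be revised. The endpoint's post-implant V70 is itself a late core-lab simulation; what certainly exists earlier is the post-implant CT and the site's plan. This objection stands: the documents permit outcome-aware reading but do not describe it.

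A reader might also infer that the plan contradicts its promise of non-biased evaluation. It does not. Section 2.3.6.2 states an aim, and the missing procedure leaves that aim unsupported.

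Reading order is usually core-lab procedure, and a core-lab charter was not supplied. The contouring instructions are a separate document, listed in SAP section 2, and could hold a safeguard. This stands in part. Protocol section 2.2.4 addresses those instructions to sites, so they may not govern core-lab reading, and neither the protocol nor the SAP points to a rule elsewhere. The documents also do not say whether the core lab or the site draws the rectal contours.

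Finally, a lock is only a partial remedy. Only Balloon Group subjects have a pre-implant CT, so its existence reveals the arm. A lab inclined to read all baselines high could still do so. After the lock, the post-implant plan is made with the balloon visible and the denominator known. All of this stands and limits what the fix can claim.

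**Conclusion.** The concern holds as a missing safeguard. Nothing in the protocol or SAP prevents the pre-implant V70 from being contoured, planned or revised with knowledge of the post-implant scan, and the visible-balloon reason does not cover the pre-implant CT.

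The size of any resulting bias cannot be derived from the documents. The type I error range of 4% to 40%, against 1.6%, rests on an assumed SD of 0.6 to 1.0 and an assumed inflation of 5% to 15% in every baseline. It shows only that the test reacts strongly to modest baseline inflation. It should not be cited as the effect of reading order or as something a lock would fully remove.

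The change is worth making because it closes one route to bias in a single-arm co-primary test at almost no cost, and it cannot be added once both scans have been read.

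**What to change.** 1. **Reading order.** In protocol section 2.2.5.2, and by reference in SAP section 10.3.4.2.1, require the core lab to contour, plan and lock each pre-implant simulation, with a time stamp, before that subject's post-implant CT is released to the reader. The locked value is analysed. Any later change is logged and both values are kept. If the core-lab charter already says this, a cross-reference is enough. Batch work near the end of the study can stay, provided this order is kept for each subject.
2. **Blinding statements.** Narrow protocol section 2.2.5.1 and SAP section 5 together, so that the SAP does not keep the broader waiver. Suggested wording: *The core lab cannot be masked to study arm, or to the balloon on post-implant CTs. It reads each pre-implant CT without access to the post-implant scan.*
3. **Limits.** State that arm cannot be masked on the pre-implant read, because only Balloon Group subjects have that scan. State also that the lock stops outcome-aware choice or revision of the denominator, but not a general upward bias in baselines or bias in the post-implant plan.

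Cost: a sequencing rule and audit trail in the core-lab procedure, plus short edits in both documents. No extra scan, reader or subject is needed, and sample size, alpha and power do not change.

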2.2.5.3 Study Duration

Each subject will be followed until the last enrolled subject is theoretically due for his 6month visit, or until follow-up is no longer required for marketing approval, whichever is earlier.

For the purposes of this study, subjects will be evaluated Pre-operatively; at Implantation; Post-implantation; weekly during IMRT Visits (no window); at 6 months post marking/balloon implantation (± 2 weeks) and every 6 months thereafter (± 4 weeks) until the last subject enrolled has completed his 6 month evaluation.

2.2.6 STUDY PROCEDURES

2.2.6.1 INFORMED CONSENT

Only prospective subjects who sign Informed Consent will be allowed to participate in this clinical study. The consent must be provided by the subject. Subjects who do not speak English must be provided a copy of an IRB approved consent in their native language, or (if

the process is approved by the site's IRB) an IRB acceptable translator. The original signed consent will be retained in each subjects study file.

2.2.6.2 VISIT WINDOWS

- Pre-implantation windows vary from 2 to 30 days.
- Post-implantation imaging no sooner than 3 days post implantation and sufficiently prior to planning to allow time for image processing.
- IMRT planning must occur after imaging and no later than 21 days post marking.
- IMRT treatments must begin no more than 24 days after marking/ implantation.
- Weekly data recording has no window.
- Follow-up at the 6 months window is ± 2 weeks.
- Follow-up for all subsequent visits is ± 4 weeks.

2.2.6.3 **CTs**

CT will be taken for the *Balloon Group* up to 30 days pre-implantation, post-implantation, at the last XRT visit and at the 6-month F/U visit. Additionally, CT may be taken in the Balloon Group at 12 months if remnants of the balloon remain at 6 months.

A CT will be taken in the *Control Group* post-implantation.

Group	Up to 30 Days Pre-Implantation	Post- Implantation	Last X-RT	6 Mo	12 Mo (if needed)
Balloon	Х	Х	Х	Х	X
Control		Х			

2.2.6.4 Pre-Implantation Evaluations and Data Collection

Data collection will include:

2.2.6.4.1 MRI

MRI to demonstrate that cancer is locally confined or extracapsular with no posterior extension may be taken up to 9 months prior to screening for patients who have very-low or low-risk prostate cancer (T1c or T2a, Gleason less than or equal to 3+3, and PSA less than 10 ng/mL). For all others, the MRI must be taken no greater than 6 months prior to screening.

2.2.6.4.2 Prior to Marking/Balloon Implantation

Within 90 days prior to marking/balloon implantation:

• Medical History and Physical Examination;

- Enrollment of patients meeting all criteria;
- CT scan taken as described in 2.2.4 for the Balloon Group (following randomization);
- Medications currently taken and
- Expanded Prostate Cancer Index (EPIC).

Within 30 days prior to marking/balloon implantation:

• Randomization.

Medical history will include descriptions of prior conditions and treatments, especially if related to the prostate, bladder, rectum, anus or perineal area; and current pain medications and other drug therapies indicated for treatment of prostate cancer.

2.2.6.4.3 Two (2) Days Prior to Marker/Balloon Implantation

• Broad-spectrum antibiotic for 5 days, starting two (2) days prior to marker/balloon implantation (*BOTH Groups*).

2.2.6.5 BALLOON AND MARKER IMPLANTATION, EVALUATIONS AND DATA COLLECTION

Prior to the implantation procedure subjects in *BOTH Groups* will receive an enema per center standard for marking the prostate and may receive medication to relieve anxiety. This should be recorded in the medications eData file.

For the *Balloon Group*, urethral catheterization is recommended at the beginning of the implantation procedure to drain the bladder and aid the positioning of the balloon. At the end of the procedure (or per local standards) the catheter should be removed.

The term "Investigator" refers to the radiation oncologist who is in charge of the planning and the IMRT treatments. However, the implantation procedure may be done by the radiation oncologist, or by a urologist who is proficient in performing transperineal procedures via transrectal Ultrasound guidance. Additionally, Investigator performing the simulation may be done by an oncologist, a medical physist, or other qualified person

This protocol requires prostate marking for *all subjects* in both study arms (*Control and Balloon Groups*). Therefore, this visit must be carried out at the location where the marking is usually done by the respective center (OR, Brachytherapy suit, etc.) by the same physician that will be inserting the balloon.

For *both groups*, the marking *MUST* be done transperineally (not transrectally). This technique will avoid potential puncture of the balloon by a marker in the *Balloon Group* and minimize the potential for data bias due to different insertion techniques.

Note: the enema must employ the same protocol for prepping the rectum as would be employed if the marking was being performed transrectally.

The insertion of the balloon will be done using a free-hand approach with the aid of a trans rectal US. Any form of anesthesia may be utilized at the discretion of the implanting physician. However, whenever possible, each center should remain consistent with the choice of anesthesia to avoid potential differences in temporary post-operative sequelae. The subject may receive local, spinal or general anesthesia. However, the subject should be at least relaxed medically to prevent accidental movement.

For Balloon Group subjects, the balloon implantation will be performed after the marking, and will be performed by a urologist/physician who will be trained by the company for balloon insertion.

Also, at the end of the implantation the operator will perform a digital rectal examination (DRE) looking for any irregularities and to exclude any suspicion of injury to the rectum. If the DRE suggests injury, an anuscopy must be used.

For *both study arms*, the implantation visit begins at the time the subject is admitted to the ambulatory setting and continues through discharge from the facility. Implantation evaluations and data collection will include:

- If excluded at this time, reason(s) for exclusion;
- Adverse events as defined by Sections 2.3.6 and 2.3.7 of this Protocol.

2.2.6.6 Post Implantation Imaging

Post-implantation imaging must occur no sooner than 3 days post implantation and sufficiently prior to planning to allow time for image processing.

2.2.6.7 IMRT Evaluations and Data Collection

2.2.6.7.1 IMRT Simulation and Planning

A CT scan as described in Section 2.2.4 must be done post implantation for **BOTH Groups**. The baseline radiation therapy (XRT) plan, and the core lab simulation, will be based on this CT. Planning must follow the contouring instructions (provided separately). Planning must occur after imaging and no later than 21 days post marking/implantation. The post-implantation simulation will be based on the planning images.

2.2.6.7.2 IMRT Treatments

In general, *for both groups*, IMRT (XRT) must start no more than 24 days after marking/ implantation. Sites will perform a weekly positioning verification using Cone beam or low dose CT scan. For the *Balloon Group*, scan results will also be used to verify balloon spacing of at least 10 mm. Subjects will receive IMRT based on the sites' dose-fractionation schedule. The following data will be captured for *both groups* during the last day of a weekly visit, for as many weeks as the treatment lasts:

IMRT Data Collection:

This data should be captured once per week on the last day of that weeks' treatment sessions during active IMRT treatment.

Weekly

- For *Balloon Group* verification of spacing status as at least 10 mm (from prostate to rectum);
- Changes in medications;
- Expanded Prostate Cancer Index (EPIC) assessment (done once at mid-point assuming the treatment plan exceeds one month (4 weeks));
- Perineal access site healing status (until healed) and
- Adverse events as defined by Sections 2.3.6 and 2.3.7 of this Protocol.

Last XRT Visit

- CT scan taken as described in Section 2.2.4 for the *Balloon*;
- Changes in medications;
- Expanded Prostate Cancer Index (EPIC) assessment and
- Adverse events as defined by Sections 2.3.6 and 2.3.7 of this Protocol.

